#### Visit 6: Follow up after 3 months +/- 10 and Fidmi device removal/replacement by balloon gastrostomy.

Prior to the procedure the patient will be asked to report his nutritional status (malnutrition defined as a body mass index [BMI] <19 kg/m^2) and any stomal complication (wound infection, peristomal leakage, hypergranulation, pressure ulcer, any skin lesion adjacent to external bumper) – all will be investigated by the study nurse using Visit 6 safety Follow Up Form. In addition patient will be asked regarding his postoperative morbidity, any other Adverse Events, Concomitant medications.

Illuminated clear photos of the insertion site will be taken:

- Frontal to the insertion site/ external bumper
- Perpendicular (from the profile) to the insertion site/ external bumper
- In close perspective if outstanding issues (medical or technical) are observed

Study nurse will also investigate tube performance: accidental dislodgement, buried bumper, gastric outlet obstruction, tube leakage, Residual Tube above skin evaluation, number of scheduled tube replacement, method of feeding (bolus, continues gravity, mechanical pump etc.), Scale 1-10 – ease of connecting the extension tube, ease of feeding, any replacements of disposable tubes other than scheduled (and reason) using Visit 6 Tube Utilization Form

ficmedical	– Study Protocol –	Protocol No.: FM-01 Version 5.1 Page 36 of 55
Safety and Usability Evaluation of the Fidmi Low-Profile Enteral Feeding Device		CONFIDENTIAL

The following assessments will be conducted prior to device removal/ replacement by balloon gastrostomy:

- a) Physical examination
- b) Vital signs

\*An endoscopic examination is not required but may be performed on a need base, and following the investigator discretion.

In case a Gastrostom replacement is required, the study investigator will advise the patient from various types of technologically equivalent or similar devices including 'low profile' types. The replacement procedure will be performed routinely as specified in the Instruction for Use.

The following assessments will be conducted following the device removal/ replacement by balloon gastrostomy:

c) PEG Physician usability Form

#### Study PEG removal Form:

Procedure duration, heart rate at the end of the operation, amount and type of analgesia consumed, postoperative bleeding, use of anti-bleeding agents (such as tranexemic acid (hexakapron)).

Endoscopist feedback Form: Endoscopist 10-point Visual Analogue Scale for removal procedure difficulty.

- d) Patient PEG removal/ replacement Feedback Form
- e) Study Patient Discharge form.

The discharging study investigator will instruct the patient (or his care giver) to immediately call the site in case of: vomiting, swollen belly, repeated abdominal aches and general deterioration (for demented patients). In case there is a suspicious of GI perforation or hemorrhage bowel obstruction the study investigator will schedule an un-scheduled visit.

C medical	– Study Protocol –	Protocol No.: FM-01 Version 5.1
		Page 37 of 55
Safety and Usability Evaluation of the Fidmi Low-Profile		CONFIDENTIAL
Enteral Feeding Device		

The patient will be asked for his most convenient day for the termination visit (Visit 7 study termination, see below) - this day will be recorded by the study nurse at the Patient Visits Log.

## Visit 7: Follow up after 4 months +/- 10, X-ray and termination visit

In compliance with the Centric Patient Approach, a home X-ray examination will be offered to the patient and his family. If chosen, a certified technician (Medix at Home, FDA and MOH approved) will visit the patient facility at the specific day scheduled together, in order to conveniently perform abdominal X-ray examination (required to verify Bumper flanges expulsion). A copy of the imaging will be provided to delegated sub-investigator for evaluation.

Following the X-ray examination, a delegated study member will call the patient facility to verify no technical issues occurred. The patient will be asked to report his nutritional status (malnutrition defined as a body mass index [BMI] <19 kg/m^2) and any stomal complication (wound infection, peristomal leakage, hypergranulation, pressure ulcer, any skin lesion adjacent to external bumper) – all will be investigated by the study nurse using Visit 7 safety Follow Up Form. In addition, patient will be asked regarding his postoperative morbidity, any other Adverse Events and Concomitant medications.

Alternatively, the patient will be admitted to the Gastrology Institute at Shaare Zedek Medical Center, Jerusalem an hour before the planned X-ray examination scheduled time accompanied by the study nurse. Prior to the examination he will be asked to report his nutritional status (malnutrition defined as a body mass index [BMI] <19 kg/m^2 and any stomal complication (wound infection, peristomal leakage, hypergranulation, pressure ulcer, any skin lesion adjacent to external bumper) – all will be investigated by the study nurse using Visit 7 safety Follow Up Form. In addition,

ficmedical	– Study Protocol –	Protocol No.: FM-01 Version 5.1 Page 38 of 55
Safety and Usability Evaluation of the Fidmi Low-Profile Enteral Feeding Device		CONFIDENTIAL

patient will be asked regarding his postoperative morbidity, any other Adverse Events, Concomitant medications.

The following forms will be completed:

- a) Post PEG removal imaging Form
- b) Termination visit

\*An endoscopic examination is not required but may be performed on a need base, and following the investigator discretion.

### Un-scheduled visit:

In case particle/s from the bumper can be seen in the imaging the discharging study investigator will instruct the patient (or his care giver) to immediately refer his caring doctor in case of: vomiting, swollen belly, repeated abdominal aches and general deterioration (for demented patients). The patient must call the study nurse to schedule an un-scheduled visit only under his caring doctor discretion of: GI perforation or hemorrhage or bowel obstruction. In such case Un-scheduled visit form will be recorded. In that kind of visit the patient will be clinically managed by the study team in the Institute of Gastroenterology and Liver Diseases until. An additional X-ray imaging will be performed to illustrate and determine the localization of the retained particles. In case of colon localization the PI will consider removing those particles by colonoscopy procedure.

Version 5.1 Page 39 of 55

Safety and Usability Evaluation of the Fidmi Low-Profile **Enteral Feeding Device** 

CONFIDENTIAL

#### Table 3 - Visit procedure chart

	Enroll and d place	evice		Follow	/ Up Per	iod	
Procedure	Screening & Enrollment	Fidmi device insertion	Sub-I visit in patient facility	Sub-I visit in patient facility	Follow up call with the patient	Fidmi device removal	X-ray and termination visit
Visits	V1	V2	V3	V4	V5	V6	V7
Time Schedule (Days)	-7	0	2	30	60	90	120
Time Window (+/- Days)	7		1	10	10	10	14
Informed consent	Х						
Demographics+ Med. history	Х						
Concomitant medications	Х	х					
Physical exam	Х	x	х	х		х	
Vital signs	Х	x	х	х		х	
Adverse event evaluation		x					
Endoscopy recording		x					
Photos of the insertion site		x	х	х		х	
PEG usability Form (physician)		х				х	
Patient Discharge form		х				х	
Safety Follow Up Form			Х	Х	Х	х	x
Tube Utilization Form (patient/care giver)			х	х	х	x	
Patient feedback Form						х	
Patient Bumper flanges							
expulsion Form							х
X-ray imaging (home/clinic)							х
Post PEG removal imaging Form							х
Termination Visit							х
Subject Visit log		Х	Х	Х	Х	х	
Un-scheduled visit Form (if needed)							

F medical	– Study Protocol –	Protocol No.: FM-01 Version 5.1 Page 40 of 55
Safety and Usability Evaluation	of the Fidmi Low-Profile	
Enteral Feeding Device		CONFIDENTIAL

#### 10.2 SCALES AND EVALUATIONS

### Physical examination

A standard physical examination will be conducted on participating patients in all study visits. These will be conducted by the investigator or by any other authorized member of the study team.

Physical examination will include weight measurements, lungs, cardiovascular system, abdomen, musculoskeletal system, skin, lymph nodes, and central nervous system and, where appropriate, other body systems per discretion of investigator (see CRF).

#### Vital signs

Vital signs (temperature, blood pressure, pulse rate, respiratory rate, and blood oxygen saturation) will be collected at all study visits.

#### Illuminated photos of the insertion site

All photos taken must be performed exactly like the previous visits- same shape and distance

\*If the patient has any lesion such as an ischemic area, gangrene, ulcer, rush, edema etc. – take at least one close photograph demonstrating the lesion. Take a new photo of every new lesion that appears through the visits.

### **11 SAFETY ASSESSMENT**

#### 11.1 Anticipated Adverse Events

Placement complication: excessive stoma wound bleeding, over tightened external bumper, gastric and/or esophageal laceration, aspiration, device unintended disassembly, need for more than one needle puncture

Post placement complication; [Time Frame: 1week-4 months]: Fever, gastric distention, infection, blockage/ occlusion, tissue necrosis, migration, erosion/embedding into the gastric wall ("Buried Bumper Syndrome"), aspiration, bleeding, fistula, GE reflux, pain, perforation, ulceration, pressure sores, skin lesion (tissue granulation) adjacent to external bumper, dumping syndrome, tube clogging, malposition, leakage, kinking, inadvertent removal, small bowel obstruction, and granulation tissue.

Post removal complication: Bowel obstruction, Bowel peroration, GI bleeding, painful defecation.

### Death after PEG procedure

fichedical	– Study Protocol –	Protocol No.: FM-01 Version 5.1 Page 41 of 55
Safety and Usability Evaluation of the Fidmi Low-Profile Enteral Feeding Device		CONFIDENTIAL

The average survival time of patients undergoing PEG insertion is 720 days (9). At Day-30 following PEG insertion, 6.5% - 19% of the patients dies from complications Predictive factors of increased 30-day mortality were higher age, lower body mass index (BMI), and the presence of diabetes mellitus. (10)

97% of death occurred following PEG insertion (30 days' time window) patients have coexistent neurologic disease. Main death causes are: cardiovascular disease, respiratory disease and central nervous system disease. (11). Most patients demonstrate multiple comorbidities and a poor functional baseline level pre-procedure.

Significant higher mortality rates (7 times higher) were observed in PEG inserted patients that were hospitalized during that time (first 30 days) compared to patients from nursing homes (12)

# 11.2 Precaution to Minimize Risk

The abovementioned risks will be minimized by having trained and qualified clinicians perform the procedure. Clinicians will be available for evaluation if there is any untoward effect.

In addition, sterile unused needles and lancets will always be used and pressure will be held at the insertion site after placing the PEG device. Further mitigations:

- Antibiotics as prescribed by the investigator
- Study nurse will provide the patient with Home instruction including emergency call (24 hours).
- Tactile Fidmi device placement/replacement and removal performed only by trained and qualified physicians.
- X-ray imaging to ensure bumper flanges expulsion
- Readiness and patient guidance for "un-scheduled visits"

# 11.3 ADVERSE EVENTS REPORTING

ficmedical	– Study Protocol –	Protocol No.: FM-01 Version 5.1 Page 42 of 55
Safety and Usability Evaluation of the Fidmi Low-Profile Enteral Feeding Device		CONFIDENTIAL

Adverse Events (AE) will be done according to National Cancer Institute (NCI) Terminology Criteria for Adverse Events v4.0 common terminology criteria for AE (CTCAE). See link for CTCAE v4.0 - (13).

AE will be collected throughout the study and recorded on the CRF. Pre-existing conditions will not be considered AEs only if they worsen beyond what would be expected. In all cases, the etiology should, as much as possible, be identified, recorded, and the Sponsor notified.

## 11.3.1 ADVERSE EVENT SEVERITTY

The severity of the AE will be evaluated by the Common Terminology Criteria for Adverse Events (CTCAE), version 4.0, for toxicity and adverse event reporting. A copy of the CTC Version 4.0 should be accessed from the CTEP site (13)- containing all NCI Common Terminology Criteria for Adverse Events (CTCAE) v.4 data files and related documents. All treatment personnel should have access to a copy of the CTC version 4.0.

Each CTCAE term is a representation of a specific event and corresponds to a single MedDRA Lowest Level Term (LLT). Grade relates to severity for the purposes of regulatory reporting and is defined as follows:

- **0.** No AE (or within normal limits).
- 1. Mild; asymptomatic or mild symptoms; clinical or diagnostic observations only; intervention not indicated.
- 2. Moderate; minimal, local, or noninvasive intervention (e.g., packing, cautery) indicated; limiting age-appropriate instrumental activities of daily living (ADL).
- **3.** Severe or medically significant but not immediately life-threatening; hospitalization or prolongation of hospitalization indicated; disabling; limiting self-care ADL.
- **4.** Life-threatening consequences; urgent intervention indicated.
- **5.** Death related to AE.

[figure not shown]
The investigator shall appoint a safety monitor who will assess the relationship of the observed symptoms to the investigational treatment. AEs will be collected

fichmedical	– Study Protocol –	Protocol No.: FM-01 Version 5.1 Page 43 of 55
Safety and Usability Evaluation	fety and Usability Evaluation of the Fidmi Low-Profile	
Enteral Feeding Device	teral Feeding Device	

from subject enrollment through follow-up period. In all cases, the etiology should, as much as possible, be identified and the Sponsor notified.

AE will be assessed by the investigator for severity, causality and outcome.

*Figure4 - AE definition (ADE- Adverse drug event, SADE-serious adverse device event)* 

## 11.3.2 ADVERSE EVENT OUTCOME

The outcome of an AE will be assessed as:

Recovered/resolved - recovered or resolved without medical sequelae. "Stop date" of the event should be the date the event is no longer present or stabilizes. If there are lingering effects after a patient is discharged then the event will not resolve until all symptoms have ceased or stabilized.

Co medical	- Study Protocol -	Protocol No.: FM-01 Version 5.1
	– Study Protocol – –	Page 44 of 55
Safety and Usability Evaluation of the Fidmi Low-Profile Enteral Feeding Device		CONFIDENTIAL

- Not recovered/not resolved for an ongoing AE for AEs that did not cause the death and were not resolved prior to the death, the outcomes for these events will be entered as "Ongoing."
- **Recovering/resolving** in the process of writing of the report
- **Recovered with sequelae/resolved with sequelae-** the nature of the sequelae • will be reported

Fatal (SAEs only) - the date of dead will be reported, the autopsy report will be given, if one will be done.

## **11.3.3 SERIOUS ADVERSE EVENT**

A serious adverse event (SAE) is any untoward medical occurrence that at any dose:

- Results in death,
- Is life-threatening. Note: The term "life-threatening" in the definition of "serious" refers to an event in which the patient was at risk of death at the time of the event; it does not refer to an event which hypothetically might have caused death if it were more severe.
- Requires inpatient hospitalization or prolongation of existing hospitalization,
- Required Intervention to Prevent Permanent Impairment or Damage (Devices)
- Medical or surgical intervention was necessary to preclude permanent • impairment of a body function, or prevent permanent damage to a body structure, either situation suspected to be due to the use of a medical product.
- Results in persistent or significant disability/incapacity, or
- Is a congenital anomaly/birth defect (not applicable to this study).

ficmedical	– Study Protocol –	Protocol No.: FM-01 Version 5.1 Page 45 of 55
Safety and Usability Evaluation of the Fidmi Low-Profile Enteral Feeding Device		CONFIDENTIAL

Medical and scientific judgment will be exercised in deciding whether expedited reporting is appropriate in other situations, such as important medical events that may not be immediately life-threatening or result in death or hospitalization but may jeopardize the patient or may require intervention to prevent one of the other outcomes listed in the definition above. These should also usually be considered serious.

#### **11.3.4 REPORTING SERIOUS ADVERSE EVENT**

Medical judgment will be exercised in deciding whether an adverse event/reaction is serious in other situations. Important adverse events/ reactions that are not immediately life-threatening or do not result in death or hospitalization, but may jeopardize the patient or may require intervention to prevent one of the other outcomes listed in the definition above, may also be considered serious .

In order to satisfy regulatory requirements, any Serious and Unanticipated Events, whether investigational product deemed related or not, must be reported to the Sponsor/ Designated CRO as soon as possible after the investigator or coordinator has become aware of its occurrence. The SAE form completion and reporting must not be delayed even if not all of the information is available at the time of the initial contact.

The Serious Adverse Event (SAE) form should be submitted within 24 hours of becoming aware of the event to the Sponsor/ Designated CRO.

Additional information (follow-up) regarding any SAE unavailable at the initial reporting should be forwarded by the site within 24 hours of the information becoming available to the Sponsor or designee.

Serious adverse events should be reported by the site to their EC/IRB as dictated by their hospital policies and procedures using Matarot clinical study designated software.

ficmedical	– Study Protocol –	Protocol No.: FM-01 Version 5.1 Page 46 of 55
Safety and Usability Evaluation of the Fidmi Low-Profile Enteral Feeding Device		CONFIDENTIAL

Subjects who have had an SAE during the treatment period may be followed clinically until all parameters (including laboratory) have either returned to normal or have stabilized or are otherwise explained. The investigator is responsible for the ongoing safety assessment of the investigational products. The Sponsor shall inform all the parties involved in the conduct and approval of the trial, i.e. the Investigators, IRBs and the Ministry of Health, of findings that may affect the safety of trial participants, or findings which have implications on the method of trial conduct, or findings that may affect the decision of the parties that approved the trial. The investigator is responsible for the ongoing safety assessment of the investigational products. The Sponsor shall inform all the parties involved in the conduct and approval of the trial, i.e. the Investigators, IRBs and the Ministry of Health, of findings that may affect the safety of trial participants, or findings which have implications on the method of trial conduct, or findings that may affect the decision of the parties that approved the trial.

### **11.3.5 SERIOUS ADVERSE DEVICE EVENT**

Any serious adverse event somehow related to treatment with the investigational product.

### **11.3.6 POST-TRIAL EVALUATIONS**

Patients who have moderate or severe on-going adverse events at the completion of the study will be advised to consult their personal physician if the event is not considered to be related to the index hospitalization. An un-scheduled visit will be arranged to manage the problem and to determine the severity and duration of the event, if it is considered to be related to the investigational device. If appropriate, specialist review within the MOH will be arranged.

ficmedical	– Study Protocol –	Protocol No.: FM-01 Version 5.1 Page 47 of 55
Safety and Usability Evaluation of the Fidmi Low-Profile Enteral Feeding Device		CONFIDENTIAL

## 12 STATISTICAL ANALYSIS

This study is an early feasibility research to primarily test the safety and usability of the investigated device.

All data obtained in this study and documented in the Case Report Forms will be listed and tabulated with descriptive group statistics (mean, standard deviation, minimum, maximum, number of valid cases), as appropriate.

For continuous variables such as age, body weight, vital signs, etc. descriptive group statistics (n, mean, standard deviation, minimum, maximum and number of valid cases), will be used as appropriate. For categorical discrete variables data, such as sex, number of Adverse Events (occurrence, severity, relationship with), etc., frequency and percentage will be computed.

Incidences of AEs will be presented by MedDRA system class, intensity, seriousness, and relation to study investigational product.

fich medical	– Study Protocol –	Protocol No.: FM-01 Version 5.1 Page 48 of 55
Safety and Usability Evaluation of the Fidmi Low-Profile Enteral Feeding Device		CONFIDENTIAL

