Inclusion/ Exclusion Criteria	
 
Exclusion Criteria:
 
Pregnancy (all women of child-bearing age would be questioned and told by the consenting physician regarding that criteria).
 
All current practice PEG contraindication
 
Acute gastrointestinal bleeding
 
Extreme obesity patients (BMI>40)
 
Emergency endoscopy
 
Infectious disease local or systemic (e.g sepsis, pancreatitis)
 
Known esophageal pathology (e.g stenosis, eosinophilic esophagitis, varices, achalasia, reflux)
 
In case of PEG replacement: lack of a well healed gastrostomy or Infection around the insertion site.
 
Known gastric pathology that may prevent safe device insertion, feeding, removal and Bumper flanges expulsion according to the investigator discretion.
 
Any history of bowel obstruction, pseudo-obstruction.
 
Crohn's disease
 

fic	edical M	– Study Protocol –	Protocol No.: FM-01 Version 5.1 Page 10 of 55	
Safety and Usability Evaluation of the Fidmi Low-Profile Enteral Feeding Device		CONFIDENTIAL		
	
 
12. Severe GERD, recurrent vomiting
 
13. Inability to tolerate sedated upper endoscopy due to cardic pulmonary instability or other contraindication to endoscopy
 
14. Current enrollment in an investigational drug or device study o participation in such a study within 30 days of entry into this study
 
			copy e study or
Study Duration	Per Patient: between 120 days±14 days, depending on the interval between pre-operative visit (inclusion) and day of operation. Total 8 months to recruit and treat 15 patients.			
Statistical Analysis Plan	NA. Feasibility safety study. Descriptive statistics will be provided.			

ficmedical	– Study Protocol –	Protocol No.: FM-01 Version 5.1 Page 11 of 55
Safety and Usability Evaluation Enteral Feeding Device	CONFIDENTIAL	

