Problem #1: Frequent dislodgement. During their total lifetime, 12.8% cases (2) of PEG tubes with soft inner bumper undergo accidental dislodgement, as patients may pull out the tube or the long tubing is displaced during patient transfers, physical therapy or by catching on sheets or bed railings. If a PEG tube is dislodged prior to the tract maturation, specifically within the first 30 days after initial placement, then an emergency intervention is required to recover the stoma. Complications within the procedure are likely to affect the stomach that can separate from the abdominal wall with the open gastrostomy leaking gastric contents into the peritoneal cavity. Delayed dislodgements have to be treated with the PEG tube being reinserted urgently (within the next 12 hours) to prevent the abdominal stoma from closing. The procedure must be undertaken in the hospital, adding workload to the patients and the healthcare system. PEG pull-outs require an emergency department visit, a level 3 surgical procedure, a replacement gastrostomy tube, and a radiographic confirmation of tube positioning. (2).

Problem #2: Difficult replacement. Physicians recommend changing standard PEG tubes after an average period of 6 months. The replacement is performed in a hospital room by pulling out the tube. It is a very painful and unpleasant procedure. Internal bumpers are not very soft to avoid issues with dislodgement and therefore the "pull" technique" is harmful and risky for patients. In 7.6% of cases, there are major complications such as gastrointestinal (GI) tract perforation (3) which can lead to peritonitis, infection, GI bleeding. Minor complications such as stoma leaking and bleeding, and skin dermatitis arise in 24% of replacement cases (4).

fic medical	– Study Protocol –	Protocol No.: FM-01 Version 5.1 Page 13 of 55
Safety and Usability Evaluation Enteral Feeding Device	CONFIDENTIAL	

**Problem #3: Tube clogging.** Obstruction is a common complication of enteral tube feeding. PEG tubes become clogged during their lifetime in approximately 45% cases (5) due to difficulties in cleaning and flushing the inner cavity properly. Tube clogging happens slowly, and progressively increases the duration of the feeding from 10 minute up to 1 hour. In addition, this has unpleasant and frustrating consequences for the patient and the caregiver, and compromises nutrient delivery.

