#### 7.2 HYPOTHESIS

Insertion of Fidmi PEG device will reduce complication rate, reduce tedious patient follow up visits at the hospitals and significantly shorten the time of replacement from currently 45 minutes (in average) to 5 minutes. Above all, Fidmi device lifetime will offer 2 years' time instead of the current 3-6 months.

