#### 8.4 SAMPLE SIZE JUSTIFICATION

15 adult patients, males or females, scheduled for PEG (Newly PEG insertion and PEG replacement involving endoscopy procedure). There will be minimum of 10 Newly PEG inserted patients enrolled to the study from the overall sample size.

Due to the small sample size and study early stage, no formal sample size calculation was done for this study.

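### Section 7.2 hypothesises a lower complication rate, but 15 single-arm patients summarised by bare percentages cannot test that for the rarer quoted rates

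*Protocol*

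**What the plan says.** Protocol Section 7.2 states a directional, comparative hypothesis: "Insertion of Fidmi PEG device will reduce complication rate". It names no comparator, reference rate, margin or decision rule.

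Section 8.1 describes an open-label, single-group, early feasibility study. Section 8.4 sets the size at "15 adult patients, males or females, scheduled for PEG" and adds that "no formal sample size calculation was done for this study".

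Section 12 lists and tabulates all case report form data. Continuous variables get "descriptive group statistics (n, mean, standard deviation, minimum, maximum and number of valid cases"; for categorical data, including adverse events, "frequency and percentage will be computed". No interval is mentioned. The synopsis row for the statistical analysis plan reads "NA. Feasibility safety study. Descriptive statistics will be provided".

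Section 5.1 supplies the rates a reader would set beside the results: "12.8% cases (2) of PEG tubes with soft inner bumper undergo accidental dislodgement" (over the life of the tube); "In 7.6% of cases, there are major complications" at replacement; minor complications in 24% of replacements; and clogging in 12.5% to 45% over tube life.

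**The concern.** The hypothesis asks whether complications are fewer than with current devices. The planned output is a percentage from at most a few events in 15 patients, with nothing to show how imprecise it is. Accidental dislodgement to 3 months is the first primary performance endpoint in the synopsis, and its counterpart in the background is 12.8%. A reported 0 of 15 (0%) would carry no sign that it is compatible with that figure. At stake is what the trial may conclude about Section 7.2, not whether it should be run.

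**Working it through.** The protocol gives no power, significance level, interval or derived sample size, so there is no figure of its own to reproduce. The 95% level below is an assumption; one-sided limits are shown where they help.

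**Inputs.** n = 15 (Section 8.4). Reference rates 7.6%, 12.8%, 24% and 12.5% to 45% (Section 5.1). Expected losses of about 20% from death and a further 20% from withdrawal (Section 9.2.4).

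**Interval for zero events.** The exact (Clopper-Pearson) two-sided upper limit for 0/n is 1 − 0.025^(1/n); the one-sided limit is 1 − 0.05^(1/n).
- 0/15, two-sided: 1 − 0.025^(1/15) = 21.8%
- 0/15, one-sided: 1 − 0.05^(1/15) = 18.1%
- For comparison, 1/15 gives 0.2% to 31.9%.

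**Chance of zero events in 15 at each quoted rate, (1 − p)^15, and whether 0/15 excludes that rate.**

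| Quoted rate p | Chance of 0/15 | Excluded by 0/15? |
|---|---|---|
| 7.6% major, at replacement | 0.924^15 = 30.6% | No |
| 12.5% clogging, low end | 0.875^15 = 13.5% | No |
| 12.8% dislodgement | 0.872^15 = 12.8% | No |
| 24% minor, at replacement | 0.760^15 = 1.6% | Yes, narrowly |
| 45% clogging, high end | 0.550^15 = 0.01% | Yes |

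That the chance for 12.8% is itself 12.8% is a coincidence.

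**Patients needed for zero events to exclude a rate.** This is the smallest n with 1 − 0.025^(1/n) below p (one-sided version in brackets).
- 7.6%: 47 (38)
- 12.8%: 27 (22)
- 24%: 14 (11)

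The exclusion of 24% therefore needs 14 evaluable patients on the two-sided limit.

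**Time frame.** The 12.8% is a tube-lifetime rate, while the endpoint stops at 3 months. Section 5.1 gives about 6 months as the life of a standard PEG tube. Assuming a constant hazard over those 6 months:
- 3-month rate = 1 − (1 − 0.128)^(3/6) = 1 − 0.872^0.5 = 6.6%
- chance of 0/15 = 0.872^(15 × 0.5) = 0.872^7.5 = about 36%

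With no time adjustment the chance is 12.8%, so the range is about 13% to 36%.

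**Attrition.** If leavers are not replaced, 15 × (1 − 0.20 − 0.20) = 9 complete. The upper limit for 0/9 is 1 − 0.025^(1/9) = 33.6%. The chance of zero events at 12.8% is 0.872^9 = 29%. With 9 patients, 24% is no longer excluded; 45% still is.

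**The case against.** The strongest reply is that this is an early feasibility study that disclaims inference: it is labelled so, has no formal sample size calculation and promises only descriptive statistics. That is a legitimate design for a first-in-human device study of 15 patients, and this stands. Descriptive analysis is not itself an error. The mismatch lies with the wording of Section 7.2.

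A reader might infer that the protocol would count zero events as support for its hypothesis. It does not say so: there is no decision rule and no stated comparison with 12.8% or any other rate.

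A reader might also infer that 15 patients can exclude none of the quoted rates. That is wrong: 0/15 would exclude 24% and 45%.

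Nor does the plan stop at means and percentages. Minimum, maximum, number of valid cases and full listings are already included, so there is no good ground here for objecting to the continuous-data summaries.

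Intervals are commonly left to a separate analysis plan. The synopsis row weakens that defence, because it marks the analysis plan as NA and does not point to a later document. The abbreviation list expands NA as not available, so the entry is not proof that no such plan exists.

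Finally, Section 9.2.4 says leavers will be replaced, which would keep the number near 15. The next sentence speaks only of patients who stop before placement, at the investigator's discretion, so the scope is unclear. Patients who leave after placement also contribute some follow-up. The figure of 9 is one end of a range.

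**Conclusion.** The point holds as a mismatch between Section 7.2 and the design and analysis in Sections 8.4 and 12. For dislodgement (12.8%) and major complications at replacement (7.6%), not even zero events in 15 could separate the device from the quoted rate. The upper limit is 21.8%, and about 27 and 47 event-free patients respectively would be needed.

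The time-frame mismatch for dislodgement strengthens the point under the constant-hazard assumption. For minor complications (24%) and the top of the clogging range (45%), zero events in 15 would be informative, the former only if at least 14 patients are evaluable.

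These results assume independent patients, a two-sided 95% level and literature rates that apply to this population. The protocol establishes none of these.

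**What to change.** 1. In Section 12, add that each participant-level event rate will be reported with its evaluable denominator and an exact (Clopper-Pearson) 95% interval. Such an interval is still descriptive and needs no larger sample.
2. Reword Section 7.2 so that fewer complications is an expectation motivating the device, which this study does not test.
3. State that the results are not a formal comparison with the literature rates in Section 5.1. If any such rate is shown beside a result, name it and give its time frame.

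The cost is a few sentences, with no change to conduct, sample size or data collection. The real price is that the results will look less favourable: 0% would be printed beside an upper limit of about 22%, or about 34% if only 9 patients are evaluable.
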